- *Fibroblast Growth Factor-21: An Adjunct Biomarker for Early Detection of Non-Alcoholic Fatty Liver Disease in Children* (IRB Protocol: 206278): Eighteen subjects, between the ages of 10-17 years completed this study between November 2017 and January 2019, were found to have NAFLD via magnetic resonance imaging. Of these, participants for whom consent was obtained to be contacted for future studies and have their information or samples used for future research may be recruited.
- *Liver Assessment via FibroScan* (IRB protocol: 260576): Participants will be recruited based on their FibroScan results (i.e. CAP score of 241 dB/m or greater). Of these, participants for whom consent was obtained for contact for future research, use of information obtained over the course of this study in future research studies related to liver and/or metabolic health, and use of information obtained over the course of this study for screening purposes for other studies related to liver and/or metabolic health, may be recruited.

Information from the AC medical records regarding a participant's contact information, demographics, and health, including medical history, medical diagnoses, medicines, puberty, date of birth, anthropometrics, vital signs, blood and imaging results, and other test results and labs may be collected upon consent/assent. This information may be collected, retrospectively (i.e., collection of information already present in the medical record at the time of enrollment) and prospectively (i.e., collection of new information that may become available after study enrollment), from the time of study enrollment up to the time that data analysis for this study is complete and results have been published (up to 3 years from enrollment).

Inclusion Criteria for Initial Enrollment:

- Ages 13-18 years (inclusive) for both sexes
- Any ethnic/racial background
- English speaking competence
- Obesity (BMI \geq 95th percentile for age and sex)
- Low risk to participate in an exercise program during initial phone screening
- Late stages of puberty (i.e., Tanner stage IV or V)
 - Female participants should have attained menarche. By definition, onset of menstrual cycles corresponds to a minimum of Tanner stage IV breast development in females. A verbal confirmation of the attainment of menstrual cycles will be enough.
 - For male participants, a verbal confirmation of late puberty signs (e.g., facial hair growth, deepening of the voice, completed linear growth) will be enough for initial enrollment. However, pubertal assessment will be conducted by the study physician upon consent/assent to confirm late pubertal status (see above).

Inclusion Criteria to Continue in the Study:

- Cleared for physical activity
- Presence of NAFLD as determined by FibroScan CAP score or MRI (see above)
- Confirmed lack of diabetes as determined by OGTT (see above)
- Confirmed late stages of puberty (i.e., Tanner stage IV or V) (see above)
- Confirmed eligibility per medical history (see above)

Exclusion criteria:

- Pre-pubertal or early stages of puberty
- Pregnancy (verbal assessment)
- Confirmed lack of NAFLD in the past 6 months via biopsy, FibroScan or MRI
- Presence of an implantable medical device or metal objects in the body (a contraindication for FibroScan)

- High-risk to participate in an exercise program as determined by “The Physical Activity Readiness Questionnaire for Everyone” (see above)
- Unable to cooperate with study procedures and tests as determined by study PI, including genetic or physical conditions impacting mobility over the past year
- Having known chronic illnesses/disorders that may independently affect study outcome measures: type 1 diabetes mellitus, T2D, neurologic (e.g., epilepsy), developmental (developmental delay, autism spectrum disorder), endocrine (Cushing’s, growth hormone deficiency), hepatic (other than NAFLD), autoimmune, cardiac and renal disorders
- Taking any of the following medications that can affect study outcome at the time of enrollment: insulin, metformin or any other anti-diabetics, antipsychotics, oral steroids, and anabolic drugs (growth hormone replacement therapy, testosterone, and oxandrolone). The participant will not be excluded from the study if he/she begins them during the study unless recommended otherwise by the primary physician.
- Adolescents who have a history of claustrophobia.
- Adolescents who need sedation in order to complete MRI.
- Adolescents determined ineligible by the PI or delegated staff.

Risks and Benefits

Subject Confidentiality: A risk to study participants is the potential for loss of confidentiality of study data. Measures to protect the confidentiality of study data will be implemented as described in the Data Handling and Recordkeeping section below.

Blood Sampling and OGTT: There is a small risk that participants will encounter bruising and/or infection after having blood taken, however, the use of well-established blood draw techniques, and antiseptic procedures will ensure minimal risk. Participants may also experience sickness or dizziness. Oral glucose tolerance test is routinely used in the clinics to screen for diabetes in at-risk individuals. There is no known risks of glucose drinks. If a subject is identified having diabetes via OGTT, appropriate referrals will be arranged and care will be provided without further delay.

FibroScan: There are no risks to having a FibroScan done. It is not invasive and is painless. It is similar to an ultrasound scan. Pregnancy is not a contraindication for FibroScan; however, pregnancy-associated physiological changes in liver structure may alter the results of FibroScan.

A TE score greater than 8.5 kPa was previously shown to be associated with advanced stages of fibrosis. If we identify any subject with a TE score of 8.5 kPa or greater, we will consult the results with [name], who is an experienced hepatologist at the UAMS GI clinic and the co-investigator of this study, for further guidance.

Dual-Energy X-ray Absorptiometry (DXA): This procedure will be used to determine body composition, and it exposes subjects to a very low dose of radiation (x-rays). The dose is only slightly greater than normal background radiation levels and is far less than that received during a standard chest x-ray (DEXA: < 0.1 mrem, Chest x-ray: 25 mrem). Otherwise, there are no known risks associated with the performance of this procedure. Because of the use of radiation, this procedure may pose risk to an unborn child.

Fitness Test and HIIT exercise: During the fitness test and HIIT exercise sessions, participants may experience discomfort associated with exercise which is normal. However, this and any other procedure can be aborted at any time at the request of the participant. The United States Centers for Disease Control and Prevention (CDC) and The American Heart Association (AHA), recommend that children be physically active for at least 60 min per day with moderate- or

vigorous-intensity in their aerobic activity.^{70,71} These entities stress that vigorous-intensity aerobic activity should be included on at least 3 days per week. In the event of an adverse event or unanticipated problems, this will be reported to the study PI, the IRB, and the study sponsor in accordance with IRB Policy 10.2.

Magnetic Resonance Imaging: MRI is a safe and painless test that uses a magnetic field and radio waves to produce detailed pictures of the liver and identify hepatic fat content. It does not give radiation. During the procedure, a participant needs to stay still as much as possible to prevent distortion of the images. Because the MRI scanner we use generates a strong magnetic field, people with metal implants (e.g., cochlear implants, cardiac pacemakers, certain prosthetic devices, etc.) are not eligible to participate in this study. Individuals with claustrophobia will be rejected as well because the risk of giving sedation outweighs the potential benefits from participating in this study. ACH Radiology Department is a very well-established site for imaging in children; therefore the risk is minimal.

Flow-Mediated Dilatation: The risks are no more than what happens in everyday life, or in a routine physical examination where blood pressure is measured. The procedure may be uncomfortable, because the blood pressure cuff will stay inflated tightly on the participant's arm for 5 minutes, which is longer than in a typical visit to the doctor. There may be some discomfort, like the hand feeling cold and feeling like it is "asleep" from the blood pressure cuff since it will be applied tightly on the forearm.

Subjects may directly benefit from participating in this study. As stated above, exercise is one of the mainstays of the NAFLD treatment. Participants will receive supervised exercise training from an experienced exercise trainer, or exercise physiologist. The knowledge gained from the study will shed light on the effect of HIIT exercise on NAFLD outcomes in adolescents. Findings from this study may help designing individualized physical exercise regimen for the patients with NAFLD.

Data Handling and Recordkeeping

The principal investigator, co-investigators, and study staff will complete and maintain appropriate CITI training. All study subject material will be assigned a unique identifying code or number. The key to the code and participants' study data will be kept in locked file(s), and/or secure UAMS and/or Arkansas Children's maintained server(s) and/or database(s) (e.g., REDCap). All data and communications will be recorded in standardized paper and/or electronic case report forms. Data will be collected and managed using REDCap. The data integrity will be password protected. Only study investigators and staff will have access to the code and information that identifies the subject in this study.

The Principal Investigator will carefully monitor study procedures to protect the safety of research subjects, the quality of the data and the integrity of the study. In addition, the PI and primary mentor ([name]) will review the data on a quarterly basis together. The information gained from this study that can be linked to a subject's identity will not be released to anyone outside of the study team other than the subject, subject's parent, and the subject's physician (if applicable). The results of this study may be published in scientific journals and/or presented at scientific meetings and conferences without identifiers. All procedures will be performed by appropriately trained and credentialed personnel supervised by the PI.

Coded samples and/or information may be shared for the purposes of this study (i.e. within the purview of this protocol) with local collaborators (e.g., Arkansas Children's Nutrition Center, Arkansas Children's Research Institute, University of Arkansas for Medical Sciences, Arkansas Children's Hospital) and/or non-local collaborators. At the conclusion of the study, the data will be stored to inform future proposals, grants, protocols, and procedures. The key to the code will

not be destroyed while information and/or samples are kept. If consented, information and/or samples may be used in future studies related to liver and/or metabolic health.

Specimen Handling and Storage

Samples will be stored in freezers in the Arkansas Children's Nutrition Center and/or Arkansas Children's Research Institute. The freezers are constantly monitored to ensure that the proper temperature is maintained. Samples will be identified using the subject's unique study acronym along with the date of sample collection and type of sample (e.g. EDTA plasma, serum). Remaining samples may be stored indefinitely or until used up for future analyses. If consented, samples may be used in future studies related liver and/or metabolic health. Participants and/or parents may contact the study's principal investigator, if they choose to withdraw consent to use samples and/or information in future research. In this case, a written letter addressed to the principal investigator expressing their desire to withdraw their consent would be required. If the information and/or samples have been shared or if publication of results has occurred, then we may not be able to remove information and/or samples.

Data Analysis

Exploratory data analysis will be conducted prior to formal statistical analysis. We will examine the distributions of all key variables to check for data errors and ensure that modeling assumptions are not violated. Numerical summaries including means, standard deviations, medians and histogram graphical techniques will be used for continuous variables and frequencies will be computed for categorical variables. For both aims, the primary outcome is IHTG level measured by both FibroScan and MRI, and secondary outcomes are fitness level, and various cardiometabolic disease markers (i.e.; insulin, glucose, adiponectin, etc.). The immediate (Aim 1) and sustained (Aim 2) effect of HIIT will be measured by comparing the changes in outcomes between groups using a linear mixed-effect framework with a subject-level random intercept. Changes in the outcomes are defined as difference between follow up visits (5-week and 3-month) versus the baseline. The independent variables will be group (intervention vs control), visit time (baseline, 5-week, 3-month) and their interaction term. This model specification can test the effect of intervention as well as difference between visits, while correctly account for the within-subject correlation due to repeated visits. Post-hoc contrasts of visit time between 5-week and baseline will be used to test the hypotheses under Aim 1, while contrasts between 3-month and 5-week will be used to test the hypotheses under Aim 2.

As an exploratory aim, diagnostic performance of FibroScan for the NAFLD adolescent will be determined by discriminating NAFLD status defined by FibroScan against that by MRI to calculate sensitivity, specificity, positive and negative predictive values. Additional agreement statistics such as concordance correlation coefficient and Bland-Altman plots will be provided for the continuous measurements of IHTG levels measured by both methods.

In our pilot data, the IHTG levels were 11.5 ± 5.4 percent at baseline for NAFLD subjects (N=23). With a pre-defined clinically significant change of 20% relative decrease from baseline, we expect the NAFLD subjects' fat percent will be decreased to an average of 9.2 ± 5.4 percent after HIIT intervention, which is an equivalent effect size of 0.43. In order to detect this effect size at 80% power, we will need 38 NAFLD participants in the intervention group, therefore 8 NAFLD subjects in the control group. Accounting for a 20% dropout rate and false-negative screening from FibroScan, we propose to enroll 58 subjects with NAFLD. Therefore, we need to screen no less than 150 subjects at-risk for NAFLD at baseline, to be able to identify 58 subjects with NAFLD (NAFLD prevalence was 40% in our pilot study, see preliminary data section above).

Ethical Considerations

This study will be conducted in accordance with all applicable government regulations and the University of Arkansas for Medical Sciences research policies and procedures. This protocol and any amendments will be submitted and approved by the UAMS Institutional Review Board (IRB) to conduct the study.

The formal consent of each adult subjects or legal representative of minor subjects and the assent of minor subjects, using the IRB-approved consent and assent forms, will be obtained before subject is submitted to any study procedure. Any subject who turns 18 years old during his/her participation in the study will be re-consented to provide his/her own consent. All subjects for this study will be provided with consent/assent forms describing this study and providing sufficient information in language suitable for subjects to make an informed decision about their participation in this study. The consent form will also be available in Spanish for Hispanic parents who do not have English speaking competence. In this instance, in-person or remote interpreter services will be available during the consent process. However, for the remainder of the study, only remote interpreter services will be available. Participants may also intermediate communications with their Hispanic parents during participation in the study.

A copy of the consent/assent may be mailed or e-mailed to parent/participant for information prior to enrollment. The person obtaining consent/assent will thoroughly explain each element of the document and outline the risks, benefits, and requirements of the study. The consent process will take place in a quiet and private room, and subjects may take as much time as needed to make a decision about their participation. Participation privacy will be maintained and questions regarding participation will be answered. No coercion or undue influence will be used in the consent process. The consent form must be signed by the subject or legally authorized representative and the person obtaining the consent, and the assent form must be signed by the minor participant. A copy of the signed consent and assent forms will be given to the participant/parent, and the informed consent process will be documented in the research record. In addition, a signed copy of the consent form may be placed in the patients' medical record. Parents/participants may also be contacted (e.g., phone, text, email, letter) during their participation in the study and/or in preparation for study visits, including prior to enrollment. During the study, parents and/or participants may withdraw study consent verbally. In this case, the subject will no longer participate in the study and no further information, data, and samples will be collected. However, we may still keep and use any information, data, and samples that have been already collected from parent and/or participant.

During the consent/assent process, parents/participants will also be given the option to allow for contact for future research, and allow for use of information and samples obtained over the course of this study in future research studies related to liver and/or metabolic health. If agreed, information and specimens will be stored indefinitely (or until used up) for potential use in future research studies. De-identified samples and information may be shared for future research use (i.e. outside the purview of this protocol) with local researchers (e.g., Arkansas Children's Nutrition Center, Arkansas Children's Research Institute, University of Arkansas for Medical Sciences, Arkansas Children's Hospital) and/or non-local researchers. In this case, samples may only be shared with researchers who do not express a plan to use them for genetic research. In addition, inquiring researchers will be informed that the stored samples do not have consent for future genetic research. Participants may choose to withdraw permission for future use of information and/or samples at any time they decide. A written letter addressed to the principal investigator expressing their desire to withdraw their consent would be required. If the information and/or samples have been shared or if publication of results has occurred, then we may not be able to remove information and/or samples. Consent for future contact and use of information and/or samples for future research will be separate from consent to participate in the

Title: Effects of High-Intensity Interval Training Exercise in Adolescents with Hepatosteatoris

PI: [name]

current study. Their decision will not affect their eligibility for this study. Participants may call the investigators or research staff to obtain more information if needed.

In addition, consent for release of data may be obtained from participants who have also taken part in *Fibroblast Growth Factor-21: An Adjunct Biomarker for Early Detection of Non-Alcoholic Fatty Liver Disease in Children* (IRB Protocol: 206278) and/or *Liver Assessment via FibroScan* (IRB protocol: 260576). If parent/participant agrees to release data, a copy of the signed consent for release of data will also be provided.

Dissemination of Data

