Based on available literature and our pilot data (shown below), **we hypothesize that insulin resistance (IR) and decreased cardiac fitness are central to the NAFLD in adolescents, and the degree of steatosis is negatively correlated with lower fitness and higher IR. Thus, exercise-driven improvements in IHTG levels will be positively associated with the increase in fitness and the decrease in IR levels in adolescents with NAFLD.** We will test our hypotheses through the following specific aims:

Aim 1: Assess the change in IHTG, and CVD and IR markers in subjects with NAFLD after 4 weeks of HIIT, compared to a sex-matched control group also with NAFLD with no training.

1A. Quantitate the change in IHTG. Hypothesis: IHTG will decrease after HIIT, and the change will be greater than that seen in controls.

1B. Measure the changes in fitness and markers of CVD. Hypothesis: HIIT will significantly increase fitness, decrease heart rate variability and blood pressure, and improve atherogenic lipid profile. The changes will be greater than that seen in controls. Changes in fitness and IHTG will correlate.

1C. Estimate changes on IR. Hypothesis: HIIT will decrease IR especially in those with higher baseline IR, and the changes will be greater than that seen in controls. Changes in IR will correlate with changes in fitness and IHTG.

Aim 2: Determine the post-intervention effects of HIIT on IHTG, and CVD and IR markers 3 months after completion of the HIIT in adolescents with baseline NAFLD.

2A. Quantitate the change in IHTG percent. Hypothesis: HIIT will have a sustained positive effect on IHTG, and that IHTG 3-months post-HIIT will be significantly lower compared to baseline level.

2B. Estimate changes on IR and other CVD markers. Hypothesis: HIIT will have a sustained positive effect on IR, and that IR 3-months post-HIIT will be significantly lower compared to baseline level.

Pediatric NAFLD has serious cardio-metabolic health outcomes. Findings of this study will inform clinical providers in the use of HIIT as a modality to treat adolescent NAFLD and associated morbidities, and produce preliminary data for mechanistic studies to probe pathways implicated in the pathogenesis of NAFLD.

Preliminary Results

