- Anthropometrics & Vital Signs: Body mass and height will be obtained using standardized techniques. In addition, we will also measure waist and hip circumferences using a tape measure. Blood pressure and heart rate will be assessed using standard techniques. If necessary, participants may be provided with a gown. Measures will be taken in duplicate, or triplicate if not within acceptable agreement.
- FibroScan: A FibroScan (FibroScan® 530 Compact, Echosens, Paris, France) will be performed to determine NAFLD status based on Controlled Attenuated Parameter (CAP) score. FibroScan, similar to an ultrasound scan, is a technique to assess liver health. FibroScan is a routinely used clinical tool in most centers to assess liver health. Outcomes of FibroScan are “Controlled Attenuated Parameter (CAP)” and “Transient Elastogram (TE)”. CAP measurement strongly correlates with steatosis, while TE measures the stiffness of the liver as a surrogate marker of fibrosis, as described above. CAP values range from 100 to 400 dB/m, and higher numbers indicate more pronounced steatosis. TE values range from 2.5 kPa to 75 kPa, and higher numbers indicate more pronounced stiffness (fibrosis). Measurement via FibroScan is done when the subject is lying down on his/her back. The test involves a probe being passed over the right upper quadrant of the abdomen to measure the liver fat content and stiffness. The results are then immediately available for review once the scan is complete. No special preparation is required before the FibroScan. We will use the CAP cut-point of 241 dB/m as suggested by Shin et al. to determine baseline steatosis.⁶⁶ A subject with a CAP score of 241 dB/m or greater will be accepted as having steatosis. FibroScan test takes about 20 minutes to complete including the generation and interpretation of the results.

In the rare instance that a valid scan is not feasible, the participant will be accepted as having NAFLD and will be allowed to proceed with the study. If upon initial Magnetic Resonance Imaging (MRI), the participant is found not to have NAFLD, then participation will be discontinued at that time.

Out of the participants whose eligibility is confirmed:

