Participants can bring a friend or family member to workout with them if they would like. A separate release will be signed by the friend or family member in order to workout at the ACNC fitness facility.

5-Week/Post-Intervention: All Subjects

Study Visit 3 – This visit may last up to 3 hours and include: measurement of body mass and height, FMD, pregnancy screening (if female), DXA, and fitness test as described above. Participants who are in the control group will complete this visit 5 weeks \pm 1.5 week after study visit 2. Participants will be reimbursed for their time with \$25 at the end of the visit.

Study Visit 4 – This visit may last up to 4 hours and include: measurement of body mass and height, vital signs, OGTT, FibroScan, urine collection, and dietary questionnaire as described above. Participants will be reimbursed for their time with \$50 at the end of the visit.

3-Month Follow-up: Exercise Group Only

Study Visit 5 – Participants from the exercise group will be asked to attend a follow-up visit 3 months \pm 2 week after last HIIT session. This visit may last up to 4 hours and include: measurement of body mass and height, hip and waist circumference, vital signs, pregnancy screening (if female), DXA, FibroScan, FMD, OGTT, urine collection, and dietary questionnaire as described above. FMD, pregnancy screening (if female) and DXA will only be completed in the instance that this visit takes place at ACNC. Participants will be reimbursed for their time with \$50 at the end of the visit.

Magnetic Resonance Imaging (MRI)

In addition to the study procedures described above, all participants will complete a MRI scan before the baseline/pre-intervention fitness test, and another MRI scan before the 5-week/post-intervention OGTT. Furthermore, participants in the exercise group will complete an additional MRI scan before the 3-month follow-up OGTT. The MRI scans will be done at the Arkansas Children's Hospital Radiology Department for the determination of hepatic fat content via magnetic resonance imaging. Each visit for completion of a MRI scan will last up to 1.5 hours. Participants will be reimbursed for their time with \$50 after each visit.

Physical Activity Assessment

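### The CAP reading that admits a participant is also the only pre-intervention CAP, so any fall in CAP from baseline within the HIIT arm includes regression to the mean

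*Combined protocol and SAP*

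**What the plan says.** Study Design and Procedures, Study Visit 1, sets the FibroScan entry rule: "A subject with a CAP score of 241 dB/m or greater will be accepted as having steatosis". The criteria to continue in the study (Study Population) require NAFLD by CAP or by MRI. There is one exception: "In the rare instance that a valid scan is not feasible, the participant will be accepted as having NAFLD". That participant is then discontinued if the first MRI shows no NAFLD.

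By the written visit lists, FibroScan is done at Visits 1, 4 and 5 and not at Visits 2 or 3. (The study design figure was not available for this check.) Visit 5 is for one arm only: "Participants from the exercise group will be asked to attend a follow-up visit 3 months" after the last session.

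Data Analysis makes FibroScan one of two primary measures: "For both aims, the primary outcome is IHTG level measured by both FibroScan and MRI". It defines change against baseline: "Changes in the outcomes are defined as difference between follow up visits (5-week and 3-month) versus the baseline". Aim 2A (Objective/Specific Aims) predicts that "IHTG 3-months post-HIIT will be significantly lower compared to baseline level". Hypothesis 1A predicts a decrease after HIIT, and one greater than in controls. Data Analysis then names a different contrast for Aim 2, 3-month against 5-week.

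**The concern.** A single CAP reading is true steatosis plus measurement error. Admitting people because that reading is at or above a cut-point favours those whose error happened to be positive. Later readings are not selected in this way, so mean CAP falls from Visit 1 even if nothing has changed in the liver. The fall is in the direction the sponsor hopes for.

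At 5 weeks both randomised arms passed the same entry rule, so the artefact cancels on average in the between-arm difference. At 3 months there are no controls to reveal it. A CAP fall from baseline in the HIIT arm could then be read as a sustained benefit, as support for the MRI result, or as a reason to doubt a null MRI result, when part or all of it came from the entry rule. The plan has no repeat baseline CAP, no repeatability figure and no mention of regression to the mean.

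**Working it through.** **Which comparisons use the selected reading**

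- HIIT, 3-month versus baseline (Aim 2A and the definition of change): uses it, with no controls. Exposed.
- HIIT, 5-week versus baseline (first half of hypothesis 1A): uses it. Exposed.
- HIIT versus control, difference in change at 5 weeks: both arms use it. Protected on average.
- HIIT, 3-month versus 5-week (the Aim 2 contrast in Data Analysis): neither scan decided entry. Not exposed.
- MRI fat, for those admitted on a valid FibroScan: the MRI reading error was not selected on. The rare participants with an invalid scan are gated on MRI instead.

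**Inputs from the documents**

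The cut is 241 dB/m, and the sample size paragraph gives 38 HIIT completers. The plan has no CAP figure to reproduce. The share passing the cut is not given either. The 40% in the sample size paragraph is the pilot MRI prevalence, and 58 of 150 screened is 38.7%.

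**Assumptions**

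CAP among those scanned is normal with total SD s_T of 40 to 60 dB/m and within-person SD s_w of 15 to 30 dB/m. There is no HIIT effect and no time trend. The test is a paired t test at two-sided 5%, because the plan states neither alpha nor sidedness.

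**Formula**

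With pass share p and a = Φ⁻¹(1 − p):

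expected false fall = (s_w² / s_T) × φ(a) / p

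The implied test-retest correlation is 1 − s_w²/s_T².

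Worked case, p = 0.40: a = 0.253, φ(a) = 0.386 and φ(a)/p = 0.966. With s_T = 50 and s_w = 20, the fall is (400/50) × 0.966 = 7.7 dB/m.

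The chance of a significant fall was simulated with 20,000 trials of 38 participants per setting. The nominal value in that direction is 2.5%.

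| Share passing | φ(a)/p | False fall over the grid (dB/m) | s_T 50, s_w 20: fall; chance | Chance over the grid |
|---|---|---|---|---|
| 40% | 0.966 | 3.6 to 21.7 | 7.7; 39% | 18% to 93% |
| 60% | 0.644 | 2.4 to 14.5 | 5.2; 20% | 10% to 61% |
| 80% | 0.350 | 1.3 to 7.9 | 2.8; 9% | 5% to 22% |
| 90% | 0.195 | 0.7 to 4.4 | 1.6; 5% | 4% to 10% |

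The low end of each row is s_T 60 with s_w 15 (correlation 0.94). The high end is s_T 40 with s_w 30 (correlation 0.44), which would be poor repeatability. With s_w no more than 20, the 40% row runs from 18% to 57%.

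**Two cross-checks**

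- The 3-month versus 5-week contrast under the same kind of model gave a mean change of zero and two-sided error of 4.5% to 5.4%.
- Study Population allows recruitment of people with an earlier CAP of 241 dB/m or more. If everyone had already passed one such scan (single-scan pass share 38.7%, correlation 0.8), the chance drops from 50% to 22%.

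**The case against.** The strongest reply is that the Aim 2 test as written is free of the artefact. Data Analysis names 3-month versus 5-week, and neither scan decided entry. That stands. A reader might infer that the planned Aim 2 test is biased by design, and the documents do not support that. But the named contrast asks whether CAP changed after training stopped. It does not test Aim 2A, which compares 3 months with baseline, as does the definition of change in the same Data Analysis section. The two sections must be reconciled, and doing so towards the stated hypothesis brings the bias in.

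The second reply is that the size is unknown. That also stands. The 40% is not a CAP pass rate, and recruiting people with an earlier high CAP, or excluding those in whom NAFLD was recently ruled out, would be expected to raise the pass share and weaken the effect. A reader might take the largest percentages as the expected error rate. They depend on a low pass share and poor repeatability, and the range begins near nominal.

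Third, dropping the formal CAP test is not the only remedy. A second pre-randomisation CAP, not used for entry, would also serve as an unselected baseline. That is correct, but it needs an extra scan of about 20 minutes per participant.

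**Conclusion.** The point holds in limited form. One scan is both the entry gate and the only scheduled baseline CAP, so within-HIIT change in CAP from baseline is shifted downwards by selection, at 5 weeks and at 3 months. The direction needs only imperfect CAP repeatability and some screened adolescents near the cut. The size rests wholly on assumed spread, repeatability and pass share. Over the grid above, the chance of a false significant fall runs from about 4% to 93% against a nominal 2.5%.

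This does not show that the 5-week between-arm comparison is biased, that baseline MRI fat is inflated in those admitted on a valid FibroScan, or that a CAP fall, if seen, would be wholly artefact. It is an inexpensive improvement to the analysis text and does not call the design as a whole into question.

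**What to change.** In Data Analysis:

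1. Reconcile the Aim 2 contrast with the Aim 2A hypothesis. State that any test of within-HIIT change from baseline (3-month for Aim 2, and the within-arm 5-week change) uses MRI fat percent only.
2. State that CAP change from the qualifying Visit 1 scan within the exercise arm is reported descriptively, labelled as including regression to the mean from the 241 dB/m entry rule, with no claim of a sustained effect.
3. Limit formal CAP inference to the HIIT-versus-control difference in change at 5 weeks and to 3-month versus 5-week within HIIT, the latter read as maintenance only.

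The cost is a few sentences, with no new visits, scans or participants. The sponsor gives up a formal CAP-versus-baseline claim, and the remaining 5-week CAP comparison rests on 8 controls. The MRI comparison at 3 months is kept, but it remains uncontrolled and should be described as such.
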